A prior study by this study team quantified nintedanib adherence trajectories using GBTMs and identified characteristics of patients associated with membership in each trajectory group. Individuals with idiopathic pulmonary fibrosis (IPF) who initiated nintedanib during 10/1/2014–12/31/2018 were identified in 100% Medicare claims and enrollment data. The sample consisted of community-dwelling older adults (≥ 66 years) with continuous coverage in Medicare Parts A, B and D for one year before (baseline) and after (follow-up) starting nintedanib. PDC was calculated for each of 12 consecutive 30-day months based on nintedanib claim fill dates and days’ supply. PDC was dichotomized, with PDC ≥ 0.8 considered adherent. A series of GBTMs of adherence was estimated to identify the best-fitting specification. Patients were then grouped based on their estimated adherence trajectories. Associations between baseline patient characteristics, including demographics, comorbidities, and health care use, and group membership probabilities were quantified as odds ratios using fractional multinomial logit modelling.

In this study, the best-fitting GBTM had five adherence trajectory groups: highly adherent (43.1%), medium adherent (11.9%), gradual decliners (10.4%), intermediate decliners (13.2%), and rapid decliners (21.5%) ([Figure 1](#)). The principal factors associated with higher odds of being in at least one of the lower-adherence groups were older age, female sex, race and ethnicity other than non-Hispanic white, and taking an additional medication during baseline.

Proprietary confidential information © 2023 Boehringer Ingelheim International GmbH or one or more of its affiliated companies

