9.2 SETTING

9.2.1 Study sites

The study will use 100% Medicare claims and enrollment data from the U.S. Medicare program on community-dwelling beneficiaries continuously enrolled in traditional, or fee-for-service, Medicare insurance coverage for inpatient hospital, skilled nursing and outpatient facility services (Part A), physician and other professional services (Part B), and outpatient prescription drugs (Part D).

The enrollment file contains monthly information on individuals' enrollment in each part of Medicare, demographic information, residential location (at the 5-digit ZIP Code level), and date of death.

Claims data are available for all medical services covered by the program and are organized into data files based on the nature and source of the claim. The Inpatient, Outpatient, and SNF files include institutional claims from hospitals for inpatient and outpatient services and from nursing homes for short-stay "skilled" admissions, respectively. The Carrier file includes fee-for-service claims submitted by professional providers, including physicians, physician assistants, clinical social workers, nurse practitioners. (Claims for some organizational providers, such as free-standing facilities are also found in the Carrier file. Examples include independent clinical laboratories, ambulance providers, free-standing ambulatory surgical centers, and free-standing radiology centers.) Separate files include claims for durable medical equipment, home health visits and hospice care.

Pharmacy Part D claims include complete prescription drug information, and all standardized prescription-level fields collected on a typical pharmacy claim (e.g., date of fill or refill, drug name and class, strength, quantity, and days' supply).

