9.3.3 Covariates

Study covariates are listed here and will be measured at the index date or during the 12 months prior.

Variable	Description
Demographic and socioeconomic characteristics	
Age	Age as of index date in years rounded to the nearest whole number will be calculated based on the difference between the beneficiary's birth date and index date.
Age group	Age group will be a categorical variable for age defined as one of 65–74, 75–84, 85+.
Female	Female will be a binary indicator for whether the beneficiary was female as indicated on the enrollment record covering the index date.
Race	Race will be a categorical variable for the beneficiary's self-reported race/ethnicity taking the

BOEHRINGER INGELHEIM Group of Companies

NIS Protocol

BI Study Number 1199-0520

Page 18 of 35

c42255024-02

Proprietary confidential information © 2023 Boehringer Ingelheim International GmbH or one or more of its affiliated companies

Variable	Description
	categories Non-Hispanic White, Black or African-American, Other, Asian/Pacific Islander, Hispanic, American Indian/Alaska Native, and unknown race from the enrollment record covering the index date.
Census region	Census region will be a categorical variable defined by categorizing the beneficiary's state of residence into Census regions (Northeast, South, Midwest, West) from the enrollment record covering the index date.
Index year	Index year will be a categorical variable defined as the year of the index date and will take the values, 2014, 2015, 2016, 2017 or 2018.
Social deprivation index	Social deprivation index will be a continuous variable ranging between 0 and 100 representing the Social Deprivation Index for the beneficiary's residential ZIP Code as calculated by the Robert Graham Center. Social Deprivation Index "is a composite measure of seven demographic characteristics collected in the American Community Survey (ACS): percent living in poverty, percent with less than 12 years of education, percent single parent household, percent living in rented housing unit, percent living in overcrowded housing unit, percent of households without a car, and percent non-employed adults under 65 years of age." This version was calculated in 2015 using data from 2015 and updates the original version created by Butler et al. (2013). Higher values for the Social Deprivation Index indicate more social deprivation.
Clinical characteristics	

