Sleep apnea	A binary indicator for whether the beneficiary had a diagnosis code for obstructive sleep apnea on at least one inpatient, outpatient or Carrier claim that occurred during the baseline period.
Lung biopsy	A binary indicator for whether the beneficiary had a diagnosis or procedure code for a lung biopsy on at

BOEHRINGER INGELHEIM Group of Companies

NIS Protocol

BI Study Number 1199-0520

Page 20 of 35

c42255024-02

Proprietary confidential information © 2023 Boehringer Ingelheim International GmbH or one or more of its affiliated companies

Variable	Description
	least one inpatient, outpatient or Carrier claim that occurred during the baseline period.
HRCT scan	A binary indicator for whether the beneficiary had a procedure code for a high-resolution computerized tomography scan on at least one inpatient, outpatient or Carrier claim that occurred during the baseline period.
Oxygen	A binary indicator for whether the beneficiary had a diagnosis, procedure revenue center code for oxygen therapy or supplemental oxygen on at least one inpatient, outpatient, Carrier, skilled nursing facility, home health or durable medical equipment claim that occurred during the baseline period.
Pulmonary rehabilitation	A binary indicator for whether the beneficiary had a procedure or revenue center code for pulmonary rehabilitation services on at least one inpatient, outpatient, Carrier, skilled nursing facility, home health or durable medical equipment claim that occurred during the baseline period.
Ventilator use	A binary indicator for whether the beneficiary had a diagnosis or procedure code for ventilator use on at least one inpatient, outpatient or Carrier claim that occurred during the baseline period.
COPD	A binary indicator for whether the beneficiary had a diagnosis code for chronic obstructive pulmonary disease on at least one inpatient, outpatient or Carrier claim that occurred during the baseline period.
Hypoxia	A binary indicator for whether the beneficiary had a diagnosis code for hypoxia on at least one inpatient, outpatient or Carrier claim that occurred during the baseline period.
Pharmacy use and spending	
Medication count	The count of the number of unique outpatient prescription medications for which beneficiary has Part D claims during the baseline period

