Total pharmacy spending	A continuous, non-negative variable representing the total amount paid by all parties for outpatient prescription medications as reported in Part D claims during the baseline period.
OOP pharmacy spending	A continuous, non-negative variable representing the total amount paid out-of-pocket by the beneficiary for outpatient prescription medications

Variable	Description
	as reported in Part D claims during the baseline period.
Inpatient hospitalization use and spending	
Any inpatient stay	A binary indicator for whether a beneficiary had at least one inpatient hospitalization for any cause during the baseline period.
Inpatient stay count	A count of the number of inpatient hospitalizations for any cause a beneficiary had during the baseline period.
Inpatient length of stay	A count of the number of days (length of stay) a beneficiary was hospitalized in an inpatient facility during the baseline period. Length of stay for each inpatient hospitalization claim will be calculated as the arithmetic difference between each claim's from and through dates.
Total inpatient spending	A continuous, non-negative variable representing the total amount paid by all parties for all inpatient hospitalizations (for any cause) as reported in inpatient facility claims during the baseline period. This is calculated as the sum of the Medicare payment amount, the Medicare per diem amount, the non-Medicare payer amount, and the patient OOP amount.
OOP inpatient spending	A continuous, non-negative variable representing the total amount paid out-of-pocket by the beneficiary for all inpatient hospitalizations (for any cause) as reported in inpatient facility claims during the baseline period.
Outpatient facility use and spending	
Any outpatient visit	A binary indicator for whether a beneficiary had at least one claim for services provided by an outpatient facility for any cause during the baseline period.
Outpatient visit count	A count of the number of unique dates with an outpatient facility for any cause claim a beneficiary had during the baseline period.
Total outpatient spending	A continuous, non-negative variable representing the total amount paid by all parties for outpatient facility claims during the baseline period. This is calculated as the sum of the Medicare payment amount, the blood deductible liability amount, the non-Medicare payer amount, and the patient OOP amount.

BOEHRINGER INGELHEIM Group of Companies

NIS Protocol

BI Study Number 1199-0520

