Page 22 of 35

c42255024-02

Proprietary confidential information © 2023 Boehringer Ingelheim International GmbH or one or more of its affiliated companies

Variable	Description
OOP outpatient spending	A continuous, non-negative variable representing the total amount paid out-of-pocket by the beneficiary for services as reported in outpatient facility claims during the baseline period.
Home health use and spending	
Any home health	A binary indicator for whether a beneficiary had at least one claim for home health services during the baseline period.
Home health count	A count of the number of home health visits a beneficiary had during the baseline period, calculated by summing the total visit count on each claim across claims.
Total home health spending	A continuous, non-negative variable representing the total amount paid by all parties for home health claims during the baseline period. This is calculated as the sum of the Medicare payment amount, the blood deductible liability amount, the non-Medicare payer amount, and the patient OOP amount.
Part B spending	
Total Part B spending	A continuous, non-negative variable representing the total amount paid by all parties for Carrier and Durable Medical Equipment claims during the baseline period, calculated as the sum of the allowed amounts on each claim.
OOP Part B spending	A continuous, non-negative variable representing the total amount paid out-of-pocket by the beneficiary for Carrier and Durable Medical Equipment claims during the baseline period.
Total spending	
Total medical spending	A continuous non-negative variable representing the total amount paid by all parties for all medical services during the baseline period, including inpatient, outpatient, home health and Part B.
Total spending	A continuous non-negative variable representing the total amount paid by all parties for all medical and pharmacy claims during the baseline period and will be calculated as the sum of total pharmacy and total medical spending.
Other use	
Any ED visit	A binary indicator for whether a beneficiary had at least one emergency department visit during the baseline visit. Note that hospitals bill for emergency department visits on either the Inpatient or Outpatient facility claims, as described by

Variable	Description
	ResDAC here. Thus, emergency department visits will be identified in inpatient and outpatient facility claims via the presence of revenue center codes 0450-0459 and 0981.

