Potential confounding by observed covariates will be addressed in two ways, thus leading to "doubly robust" estimates. The first way is to calculate two sets of observation-level weights that balance covariates across exposure categories: inverse probability of treatment weights (IPTWs) and weights derived from a marginal mean weighting through stratification (MMWS) procedure (Hong, 2012; Linden, 2014). To generate the weights, a multinomial logit model of nintedanib adherence trajectory group category will be estimated as a function of the covariate roster. Predicted probabilities (i.e., propensity scores) for each category will be generated from the model results and used to calculate both the IPTW and MMWS

Proprietary confidential information © 2023 Boehringer Ingelheim International GmbH or one or more of its affiliated companies weights. Because multiple exposure categories are to be compared, the weights will provide estimates of the average treatment effect (ATE) (and not the average treatment effect on the treated [ATT]).

The second way confounding will be addressed is through regression adjustment; that is, observed covariates will be added to the GLM specification. Combining weighting with regression adjustment yields a double robustness property that attenuates bias in the case when either the treatment model (i.e., the multinomial logit model of exposure category) or the outcome model (i.e., the GLM of the health care resource use or spending outcome) is misspecified (Linden et al., 2016).

To facilitate interpretability, the regression model results will be transformed back to the scale of the outcome variable. Average marginal effects and their 95% confidence intervals (CIs) will be calculated using the delta method. Data preparation will be performed using SAS 9.4 (██████████) and data analysis will be conducted using Stata 17 (██████████).

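### Baseline corticosteroid and immunosuppressant use is not directly adjusted for, because drug treatment enters the covariate roster only as a medication count and dollars

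*Combined protocol and SAP*

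**What the plan says.** Section 9.3.3 introduces the roster with "Study covariates are listed here and will be measured at the index date or during the 12 months prior". Its 43 rows carry drug treatment in four places:

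- Number of medications: "The count of the number of unique outpatient prescription medications for which beneficiary has Part D claims during the baseline period".
- Pharmacy spending, all payers: "the total amount paid by all parties for outpatient prescription medications as reported in Part D claims during the baseline period".
- Pharmacy spending, patient share: "the total amount paid out-of-pocket by the beneficiary for outpatient prescription medications".
- An overall spending row, which "will be calculated as the sum of total pharmacy and total medical spending".

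No row names a drug or a drug class, and corticosteroids and immunosuppressants are mentioned nowhere in the document. Non-drug treatments do have rows of their own: oxygen, pulmonary rehabilitation and ventilator use.

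In section 9.7.1, "a multinomial logit model of nintedanib adherence trajectory group category will be estimated as a function of the covariate roster", and the observed covariates are added to the GLM. Section 9.2.1 lists, among the Part D fields, the fill date and "drug name and class, strength, quantity".

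**The concern.** A count gives a corticosteroid and a statin the same weight, and pooled spending does not say what was bought. If use of these two classes before nintedanib differs between trajectory groups and also predicts later hospitalization or cost, part of a pairwise contrast would reflect prior treatment rather than adherence. That such use predicts cost in this cohort is an assumption; the document does not say so.

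The point matters more than another optional covariate would because section 9.9 concedes that claims lack determinants of cost that may be correlated with adherence, and names IPF severity. A treatment marker that may partly reflect severity is available in data the study already holds. Section 9.9 does not mention concomitant drug class.

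**Working it through.** The plan states no figure that depends on this choice, so there is nothing to reproduce. The check is a reading of the roster, followed by two illustrations with assumed inputs.

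**1. Is drug class in either model?** All 43 rows of section 9.3.3 were read. None carries it. The multinomial logit uses the roster and the GLM adds observed covariates, so a variable off the roster is off both. Section 9.7.1 claims protection when one of the two models is misspecified. A confounder missing from both lies outside that claim.

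**2. Does eligibility remove the issue?** Section 9.2.2 excludes prior antifibrotic use by drug. It excludes autoimmune and connective tissue disease by diagnosis code. The second exclusion probably removes some users of these classes, but it neither excludes nor adjusts for use among the IPF patients who remain.

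**3. Can a count stand in for a class?** A simulation used two groups and 400,000 patients. All inputs were assumed: about 25% use the class, use adds 1 to a count averaging about 10, and the odds ratio of use for lower adherence is exp(0.5), about 1.65.

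| Weighting | Class use, lower vs higher adherence | Standardized difference |
|---|---|---|
| None | 31.1% vs 21.6% | 0.22 |
| On count only | 31.0% vs 21.7% | 0.21 |
| On count and class indicator | 25.0% vs 25.0% | 0.00 |

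Weighting on the count balanced the count and left the class almost untouched. This isolates the count. It does not show what the full roster would leave.

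**4. What could a wholly unadjusted class do to a cost ratio?** With prevalence p0 in the highly adherent group, p1 in a lower-adherence group, and cost ratio R for users against non-users:

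spurious difference = [1 + (R − 1)p1] / [1 + (R − 1)p0] − 1

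The assumed ranges are p0 of 20–30%, p1 higher by 5–15 points, and R of 1.25–2.0.

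- Low end: p0 = 0.20, p1 = 0.25, R = 1.25 gives 1.0625/1.05 − 1 = +1.2%.
- Middle: p0 = 0.20, p1 = 0.30, R = 1.5 gives 1.15/1.10 − 1 = +4.5%.
- High end: p0 = 0.20, p1 = 0.35, R = 2.0 gives 1.35/1.20 − 1 = +12.5%.
- Prevalences of the high end swapped: 1.20/1.35 − 1 = −11.1%.

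Nothing is deducted here for the other covariates, and the sign depends on which group has more users.

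**5. Are the cells large enough?** Section 9.5 gives 1,798 patients. With the shares in section 9.3.1 the groups are about 775, 214, 187, 237 and 387 (the shares sum to 100.1% by rounding). Section 9.6 lets out only aggregates based on at least 11 patients. If this is read as a limit on cell counts, the smallest group needs 11/187 = 5.9% prevalence before its cell can be exported. Two indicators across four non-reference groups add 2 × 4 = 8 propensity parameters; one merged indicator adds 4.

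**The case against.** The strongest reply is that the plan already balances much of what these drugs would stand for. Recent exacerbation or infection that led to care should appear in baseline inpatient stays, length of stay, inpatient spending and ED visits. Respiratory status and specialist care are partly covered by oxygen, hypoxia, ventilator use, COPD, asthma, pulmonology visits and pulmonology prescriber. What matters is drug use conditional on all of these, not on the count alone. This stands, and it limits the point: proxies reduce the problem by an unknown amount, and a variable that is never tabulated cannot show whether they were enough.

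Two stronger readings are tempting, and the document does not support them.

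- A reader might infer that the drug classes are left unbalanced. No prevalence is given, overall or by group. Only the absence of direct adjustment is established.
- A reader might take the prior study's result in section 7, that "taking an additional medication during baseline" went with higher odds of a lower-adherence group, as evidence of confounding by these drugs. It is an association with additional medication, for which the plan has a count. It does not say which drugs are involved.

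It can also be said that any claims roster can be extended by one more class, and that section 9.9 already concedes unmeasured determinants. That is fair as to weight. It is a weaker defence where the information is in the data and costs little to use.

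**Conclusion.** The omission is real. Two drug classes that can be identified in the study's own Part D claims are adjusted for only through a count, pooled dollars and indirect proxies. The size and direction of any residual confounding are unknown. The 1.2% to 12.5% range is a sensitivity illustration with assumed inputs and no credit for the other covariates, and it turns negative if users are concentrated among highly adherent patients. It should not be quoted as the bias in this study. A reader might go further and put a dollar amount on the error, or conclude that the plan overstates the cost of non-adherence. The document contains no cost data and no prevalence by group, so it supports neither. The point rests on the assumption that these drugs predict later use or cost given the rest of the roster. It is an inexpensive improvement to confounding control, not a demonstrated failure of the analysis.

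**What to change.** Add two binary rows to section 9.3.3, both from baseline Part D claims: any systemic corticosteroid fill, and any non-steroid immunosuppressant fill. Enter them in the multinomial logit and the GLM, and report them by trajectory group before and after weighting. If cells are sparse or fall under the 11-patient limit, merge the two into one indicator. Keep the medication count.

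The cost is code lists for two classes and up to eight propensity parameters. Rare use in a small group could also produce extreme weights, which is a further reason to merge. The roster can be shortened in return: total medical spending covers the inpatient, outpatient, home health and Part B rows, and total spending adds the pharmacy row, so both repeat listed components. If these enter untransformed they are already collinear with their parts, so dropping them tidies the model more than it frees parameters.

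The indicators would capture outpatient-dispensed use only; drugs given in hospital or billed under Part B would be missed, and section 9.9 should say so. If the analysis is already fixed, given the final report date of 15 May 2023 in section 6, the minimum is to name the omission in section 9.9 and run the adjustment as a sensitivity analysis.
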